Appendix G Classification of Tumour Lysis Syndrome

G 1 Classification

The criteria for classification of laboratory and clinical TLS in adults are described below. These criteria are based on the [Howard et al 2011](#) modification of [Cairo and Bishop 2004](#), and have been adapted from [Cheson et al 2017](#).

Clinical TLS assumes the laboratory evidence of metabolic changes and an adverse event that requires clinical intervention. Clinical TLS is defined as the presence of laboratory TLS and any one or more of the clinical criteria, as specified in [Table 35](#) below.

Table 35 Criteria for Laboratory and Clinical Tumour Lysis Syndrome

Abnormality	Criteria
Laboratory TLS	
Two or more of the following metabolic abnormalities occurring during the same 24-hour period, and within 3 days before until 7 days after infusion of study treatment:	
Hyperuricaemia	Uric acid $\geq 475.8 \mu\text{mol/L}$ ($\geq 8.0 \text{ mg/dL}$)
Hyperkalaemia	Potassium $\geq 6.0 \text{ mmol/L}$
Hyperphosphataemia	Phosphate $\geq 1.5 \text{ mmol/L}$ ($\geq 4.5 \text{ mg/dL}$)
Hypocalcaemia	Corrected calcium $< 1.75 \text{ mmol/L}$ ($< 7.0 \text{ mg/dL}$), or Ionised calcium $< 0.3 \text{ mmol/L}$
Clinical TLS	
Laboratory TLS plus one or more of the following:	
Acute kidney injury	Serum creatinine increase by $> 26.5 \mu\text{mol/L}$ (or a single value $> 1.5 \times \text{ULN}$ if no baseline measurement), or oliguria (average urine output of $< 0.5 \text{ mL/kg/h}$) lasting for $> 6 \text{ hours}$
Cardiac arrhythmia/dysrhythmia or sudden death	Probably or definitely caused by hyperkalaemia or hypocalcaemia
Seizure	Probably or definitely caused by hypocalcaemia
Neuromuscular irritability, hypotension, or heart failure	Probably or definitely caused by hypocalcaemia

TLS, tumour lysis syndrome; ULN, upper limit of normal.

G 2 Grading

TLS should be graded according to the Cairo-Bishop criteria for the purposes of dose-limiting toxicity assessment ([Cairo and Bishop 2004](#)). The grade of the maximal clinical manifestation defines the overall grade of TLS, as summarised below in [Table 36](#).

Table 36 Grading of Tumour Lysis Syndrome

Cairo-Bishop Grading for TLS						
Abnormality	Grade 0	Grade 1	Grade 2	Grade 3	Grade 4	Grade 5
Laboratory TLS	Absent	Present	Present	Present	Present	Present
Serum creatinine ^a	< 1.5 x ULN	1.5 x ULN	> 1.5 – 3.0 x ULN	> 3.0 – 6.0 x ULN	> 6.0 x ULN	Death ^b
Cardiac arrhythmia ^a	None	Intervention not indicated	Nonurgent medical intervention indicated	Symptomatic and incompletely controlled medically, or controlled with device (eg, defibrillator)	Life-threatening (eg, arrhythmia associated with CHF, hypotension, syncope, shock)	Death ^b
Seizure ^a	None	--	One brief generalised seizure; seizures well controlled by anticonvulsants; infrequent focal motor seizures not interfering with ADL	Seizure in which consciousness is altered; poorly controlled seizure disorder; with breakthrough generalised seizures despite medical intervention	Seizure of any kind and prolonged, repetitive or difficult to control (eg, status epilepticus, intractable epilepsy)	Death ^b

^a Not directly or probably attributable to a concomitant therapeutic agent.

^b Probably or definitely attributable to clinical TLS.

Modified from [Cairo and Bishop 2004](#).

ADL, activities of daily living; CHF, congestive heart failure; TLS, tumour lysis syndrome; ULN, upper limit of normal.

G 3 References

Cairo and Bishop 2004

Cheson et al 2017

Howard et al 2011

Appendix H Drugs That Prolong QT Interval and/or Induce Torsades De Pointes

Drugs with known or possible risk of TdP (cardiac arrhythmia due to drug-induced QTc prolongation) are withheld for 5 half-lives prior to the first dose of study treatment and will continue to be withheld during the study, and for 14 days after the last dose of AZD0466.

Table 37 Drugs with a known risk of Torsades de Pointes

Contraindicated drug	Withdrawal period prior to the start of study treatment
Aclarubicin, anagrelide, ciprofloxacin, clarithromycin, cocaine, droperidol, erythromycin, levofloxacin, ondansetron, papaverine hydrochloride, procainamide, sulpiride, sultopride, terfenadine, terlipressin.	2 days
Cilostazol, cisapride, disopyramide, dofetilide, domperidone, flecainide, gatifloxacin, grepafloxacin, ibutilide, moxifloxacin, oxaliplatin, propofol, quinidine, sotalol, roxithromycin, sevoflurane, sparfloxacin, thioridazine	7 days
Azithromycin, bepridil, chlorpromazine, halofantrine, haloperidol, mesoridazine, citalopram, dronedarone, escitalopram, fluconazole, levomepromazine, levosulpiride	14 days
Donepezil, terodiline	3 weeks
Levomethadyl, methadone, pimozide	3 weeks ^b
Arsenic trioxide, ibogaine	3 weeks ^b
Pentamidine	3 weeks ^b
Astemizole, probucol, vandetanib	3 weeks ^b
Amiodarone, chloroquine	1 year

^a Estimated value, as pharmacokinetics of arsenic trioxide have not been studied.

^b The withdrawal period for these drugs will be 3 weeks prior to the start of study treatment, after discussion with the Medical Monitor regarding the risk/benefit ratio.

CredibleMeds® (www.crediblemeds.org) is the standard reference for drugs with known or possible risk of TdP. Since CredibleMeds® constantly assesses new drug information and updates its lists, sites should go directly to the crediblemeds.org website in real-time for reference. Patients receiving drugs listed in the “known” or “possible” categories at the time of eligibility assessment are prohibited from 14 days before the start of treatment until permanent discontinuation of treatment.

Some of the medications listed as a possible risk of TdP may be allowed at the Investigator's discretion after approval by the Medical Monitor when the patient has unmet medical need to continue receiving prohibited medication(s), no suitable alternative treatments are available, and the benefit-risk ratio is acceptable in the Investigator's opinion.

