- Reversible CYP3A inhibitors (Section 6.5.2), which cannot be discontinued within 14 days or 5 half-lives, whichever is shorter, prior to the first dose of study treatment and withheld throughout the study until 14 days after the last dose of AZD0466.
- Moderate or strong mechanism-based inhibitors or inducers of CYP3A4 which cannot be discontinued within 14 days prior to the first dose of study treatment, and withheld until 14 days after the last dose of AZD0466 (see Section 6.5.2 for a list of medications).
- Concurrent anti-coagulation therapy, including aspirin and heparin, which cannot be stopped. Heparin for vascular line management is allowed.

- Medications with known risk of Torsades de Pointes (TdP; see [Appendix H](#)), which cannot be discontinued within 5 half-lives of the first dose of study treatment and withheld until 14 days after the last dose of AZD0466. Some of the medications listed as a possible risk of TdP may be allowed at the Investigator's discretion after approval by the Medical Monitor when the patient has unmet medical need to continue receiving prohibited medication(s), no suitable alternative treatments are available, and the benefit-risk ratio is acceptable in the Investigator's opinion.

Prior/Concurrent Clinical Study Experience

15 History of hypersensitivity to polyethylene glycol (PEG), PEGylated products or drugs with a similar chemical structure or class to AZD0466 or other BH3 mimetic.

Other exclusions

16 Psychological, familial, sociological, or geographical conditions that do not permit compliance with the protocol.

17 Judgement by the Investigator or Medical Monitor that the patient should not participate in the study if the patient is unlikely to comply with study procedures, restrictions and requirements.

18 Lactating, breastfeeding, or positive pregnancy test for women of childbearing potential.

19 Involvement in the planning and/or conduct of the study (applies to both AstraZeneca staff and/or staff at the study site).

20 Persons who, due to an official directive or court order, have been accommodated in an institution, must be excluded from participation.

21 Persons who are dependents of the Sponsor, Investigator, or the study site are also to be excluded from participation.

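### Appendix H gives two pre-dose washouts for Torsades-risk drugs that disagree for 46 of the 58 drugs listed, and two end points for the restriction, without saying which governs

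*Protocol*

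**What the plan says.** The restriction on drugs that can cause Torsades de Pointes appears in two places in the protocol, Section 5.2 and Appendix H.

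- **Section 5.2, exclusion criterion 14.** It excludes patients on known-risk drugs "which cannot be discontinued within 5 half-lives of the first dose of study treatment and withheld until 14 days after the last dose of AZD0466". The same bullet then lets the investigator, with Medical Monitor approval, allow some possible-risk drugs.
- **Appendix H, opening paragraph.** Known-risk and possible-risk drugs "are withheld for 5 half-lives prior to the first dose of study treatment and will continue to be withheld during the study". The same sentence extends the hold past the final AZD0466 infusion by a further 14 days.
- **Appendix H, Table 37.** Titled as a list of known-risk drugs, it has a column headed "Withdrawal period prior to the start of study treatment". The 2-day row begins "Aclarubicin, anagrelide, ciprofloxacin, clarithromycin, cocaine, droperidol, erythromycin, levofloxacin, ondansetron"; the 1-year row is "Amiodarone, chloroquine".
- **Appendix H, paragraph after Table 37.** Known-risk and possible-risk drugs "are prohibited from 14 days before the start of treatment until permanent discontinuation of treatment".

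Section 5 requires that a patient meet none of the exclusion criteria and allows no exceptions. SAP Section 4.6.2.1 (Deviation 1) treats any dosed patient who departed from the entry criteria as an important protocol deviation.

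**The concern.** A site checking a listed drug finds a drug-specific period in the table and a flat 14 days in the paragraph below it. For most drugs the two give different answers, and nothing says which prevails, that the longest applies, or that the 14-day sentence is meant only for drugs outside the table.

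The rule decides who may be dosed, and it bears on a monitored safety signal. QTcF has an entry limit of 470 msec (Section 5.2, criterion 11) and triggers withholding (Section 6.6.5). It also feeds the Holter-based PK modelling (Section 11.6.2.6.1) and an outlier summary (SAP Section 4.14.8). If sites resolve the conflict differently, the entry criterion is not applied uniformly, and the count of eligibility deviations depends on which sentence the classifier used.

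**Working it through.** No power or error-rate figure is involved. The check compares the statements directly.

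**1. Table 37 against the flat 14 days.** Drugs were counted row by row from Table 37. The 3-week rows hold 2 + 3 + 2 + 1 + 3 = 11.

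| Table 37 period | Drugs | Table 37 minus 14 days |
|---|---|---|
| 2 days | 15 | −12 days |
| 7 days | 18 | −7 days |
| 14 days | 12 | 0 |
| 3 weeks (21 days) | 11 | +7 days |
| 1 year (365 days) | 2 | +351 days |
| Total | 58 | |

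Table 37 is shorter for 15 + 18 = 33 drugs and longer for 11 + 2 = 13. They disagree for 33 + 13 = 46 of 58 (79%).

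**2. Two patients.**

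- Ondansetron stopped 5 days before Day 1: 5 ≥ 2, so Table 37 is met; 5 < 14, so the 14-day sentence bars the patient.
- Amiodarone stopped 4 weeks before Day 1: 28 ≥ 14, so the 14-day sentence is cleared; 28 < 365, so Table 37 is not met.

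**3. Do other washouts settle it?** Section 6.5.2 has no Torsades rule. Its separate 14-day list of CYP3A inducers and mechanism-based inhibitors names clarithromycin and erythromycin (2-day row) and thioridazine (7-day row). For these three, 14 days is required anyway, which leaves 33 − 3 = 30 shorter-row drugs that this list does not settle. Section 6.5.2 names neither ondansetron nor amiodarone.

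**4. End of the restriction.** Exclusion criterion 14 and the opening of Appendix H run to 14 days after the last dose. The later sentence stops at permanent discontinuation. The gap is up to 14 days, depending on how discontinuation is dated.

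**5. Drug class.** Exclusion criterion 14 names known-risk drugs only, yet grants an exception for possible-risk drugs, which is needed only if those are restricted. Appendix H covers both classes outright.

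**6. Five half-lives against Table 37.** The table would equal 5 half-lives at half-lives of 2/5 = 0.4 days (9.6 h), 7/5 = 1.4 days (33.6 h), 14/5 = 2.8 days (67.2 h), 21/5 = 4.2 days (100.8 h) and 365/5 = 73 days. The documents give no half-lives, so this cannot be tested.

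**The case against.** The strongest reply is that the statements are prohibitions that apply together. Clearing the 14-day sentence does not make the amiodarone patient eligible, because exclusion criterion 14 and Table 37 still have to be satisfied. A site that always used the longest window would breach nothing before dosing. This stands in part: for the 13 longer-period drugs the documents show no route to enrolment. But the protocol nowhere states a longest-applies rule, and under that rule the 2-day and 7-day entries could never determine eligibility.

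A second reply is that the 14-day sentence was meant for drugs outside the table. The text does not say so, and the sentence expressly includes the known-risk category that Table 37 lists.

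A reader might also infer that there are three incompatible washouts, with 5 half-lives as the third. The documents do not support this. Table 37 sits directly under the 5-half-lives sentence and reads as its drug-by-drug implementation. Two footnotes hint at other inputs: one value is called an estimate, and some 3-week periods follow a risk/benefit discussion with the Medical Monitor. That does not establish a conflict.

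Nor do the documents show that patients will start treatment with residual QT-prolonging drug on board. That would need a site to apply the 14-day sentence alone, no residual exposure can be calculated, and triplicate ECGs at entry and on treatment give some protection.

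**Conclusion.** The point holds as an internal inconsistency in an eligibility rule. Within Appendix H, Table 37 and the 14-day sentence differ for 46 of 58 listed drugs, in both directions, and precedence is not stated. The practical ambiguity is clearest for the 33 shorter-period drugs, less the three already held to 14 days by Section 6.5.2. The end of the restriction and the drug class are also stated inconsistently between exclusion criterion 14 and Appendix H.

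This rests on two readings: that the 14-day sentence, whose grammatical subject is patients on such drugs at eligibility assessment, restricts the drugs themselves; and that it applies to Table 37 drugs because it names their category. Uneven eligibility windows and uneven deviation classification are possible consequences, not demonstrated ones. Sample size and error rates are unaffected, and no formal hypothesis test is planned.

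**What to change.** The sponsor should reconcile exclusion criterion 14 in Section 5.2 with Appendix H so that together they state:

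- which pre-dose washout governs when the statements differ (a single precedence sentence would do);
- one drug class, known-risk only or known-risk and possible-risk, with the Medical Monitor exception worded to match;
- one end of the restriction.

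Which period, class and end point to use is a clinical decision for the sponsor.

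The cost is a wording change, with no added patients or procedures. SAP Section 1 records that recruitment stopped on 16 June 2023 and that the decision to terminate was made on 28 July 2023, so an amendment may not follow. In that case the protocol deviations specification and the study report should state which rule was used to classify eligibility deviations under SAP Deviation 1.

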Appendix I Contraception Guidance

I 1 Definitions

- A female of childbearing potential is defined as a female who is not permanently surgically sterilised or postmenopausal.
- Surgical sterilisation includes hysterectomy and/or bilateral oophorectomy and/or bilateral salpingectomy but excludes bilateral tubal occlusion (the term occlusion refers to both occluding and ligating techniques that do not physically remove the oviducts).
- Postmenopausal is defined as amenorrhoeic for 12 months without an alternative medical cause. The following age-specific requirements apply:
 - Women under 50 years of age would be considered postmenopausal if they have been amenorrhoeic for 12 months or more following cessation of exogenous hormonal treatments AND with luteinising hormone and follicle-stimulating hormone levels in the postmenopausal range
 - Women over 50 years of age would be considered postmenopausal if they have been amenorrhoeic for 12 months or more following cessation of all exogenous hormonal treatments
- A highly effective method of contraception is defined as a method that results in a low failure rate (ie, less than 1% per year) when used consistently and correctly.

I 2 Contraception Methods

Highly effective methods of contraception are described in [Table 38](#).

Table 38 Highly Effective Methods of Contraception

Barrier/Intrauterine Methods	Hormonal Methods

• Intrauterine device• Intrauterine hormone-releasing system (IUS)• Bilateral tubal occlusion• Vasectomised partner ^a• Sexual abstinence ^b	
Combined (oestrogen and progestogen containing ^c hormonal contraception)
 
◦ Oral (combined pill)◦ Injectable◦ Transdermal (patch) 
Progestogen-only hormonal contraception associated with inhibition of ovulation ^d
 
◦ Injectable◦ Implantable

^a With appropriate post-vasectomy documentation of surgical success (absence of sperm in ejaculate).

^b Sexual abstinence is considered a highly effective method only if defined as refraining from heterosexual intercourse during the entire period of the study and if it is the preferred and usual lifestyle of the subject. However, periodic or occasional abstinence, the rhythm method, and the withdrawal method are not acceptable methods of contraception.

^c Hormonal contraception may be susceptible to interaction with study or other drugs, which may reduce the efficacy of the contraception method. Women using hormonal contraceptives must add a barrier method.

^d Progestogen-only hormonal contraception, where inhibition of ovulation is not the primary mode of action (eg, minipill), is not accepted as a highly effective method.

Appendix J Response Evaluation Criteria for Acute Myeloid Leukaemia

These criteria are based on the [Döhner et al 2017](#) revised recommendations of the international working group for diagnosis, standardisation of response criteria, treatment outcomes, and reporting standards for therapeutic trials in acute myeloid leukaemia ([Döhner et al 2017](#)).

Category	Definition
Response	
CR without minimal residual disease (CR _{MRD} -)	If studied pretreatment, CR with negativity for a genetic marker by RT-qPCR, or CR with negativity by MFC
Complete remission (CR)	Bone marrow blasts <5%; absence of circulating blasts and blasts with Auer rods; absence of extramedullary disease; ANC $\geq 1.0 \times 10^9/L$ (1000/ μ L); platelet count $\geq 100 \times 10^9/L$ (100 000/ μ L)
CR with incomplete haematologic recovery (CR _i)	All CR criteria except for residual neutropenia ($<1.0 \times 10^9/L$ [1000/ μ L]) or thrombocytopenia ($<100 \times 10^9/L$ [100 000/ μ L])
Morphologic leukemia-free state (MLFS)	Bone marrow blasts <5%; absence of blasts with Auer rods; absence of extramedullary disease; no haematologic recovery required
Partial remission (PR)	All haematologic criteria of CR; decrease of bone marrow blast percentage to 5% to 25%; and decrease of pretreatment bone marrow blast percentage by at least 50%
Treatment failure	
Primary refractory disease	No CR or CR _i after 2 courses of intensive induction treatment; excluding patients with death in aplasia or death due to indeterminate cause
Death in aplasia	Deaths occurring ≥ 7 d following completion of initial treatment while cytopenic; with an aplastic or hypoplastic bone marrow obtained within 7 d of death, without evidence of persistent leukemia
Death from indeterminate cause	Deaths occurring before completion of therapy, or <7 d following its completion; or deaths occurring ≥ 7 d following completion of initial therapy with no blasts in the blood, but no bone marrow examination available
Response criteria for clinical trials only	
Stable disease	Absence of CR _{MRD} -, CR, CR _i , PR, MLFS; and criteria for PD not met
Progressive disease (PD) ^{a b}	
Evidence for an increase in bone marrow blast percentage and/or increase of absolute blast counts in the blood:
 
 >50% increase in marrow blasts over baseline (a minimum 15% point increase is required in cases with <30% blasts at baseline; or persistent marrow blast percentage of >70% over at least 3 mo; without at least a 100% improvement in ANC to an absolute level ($>0.5 \times 10^9/L$ [500/μL], and/or platelet count to $>50 \times 10^9/L$ [50 000/μL] nontransfused); or >50% increase in peripheral blasts (WBC \times % blasts) to $>25 \times 10^9/L$ ($>25 000/\mu$L) (in the absence of differentiation syndrome) ^b; or New extramedullary disease
Relapse	

Category	Definition
Haematologic relapse (after CR _{MRD-} , CR, CR _i)	Bone marrow blasts $\geq 5\%$; or reappearance of blasts in the blood; or development of extramedullary disease
Molecular relapse (after CR _{MRD-})	If studied pretreatment, reoccurrence of MRD as assessed by RT-qPCR or by MFC

^a The authors acknowledge that this new provisional category is arbitrarily defined; the category aims at harmonising the various definitions used in different clinical trials.

^b Certain targeted therapies, for example, those inhibiting mutant IDH proteins, may cause a differentiation syndrome, that is, a transient increase in the percentage of bone marrow blasts and an absolute increase in blood blasts; in the setting of therapy with such compounds, an increase in blasts may not necessarily indicate PD.

ANC, absolute neutrophil count; d, day; IDH, isocitrate dehydrogenase; MFC, multiparameter flow cytometry; mo, month; RT-qPCR, real-time quantitative polymerase chain reaction; WBC, white blood cell.

J 1 References

Döhner et al 2017

Appendix K Response Assessment for Acute Lymphoblastic Leukaemia

Disease Status Criteria for acute lymphoblastic leukaemia (ALL):

At least 20% lymphoblasts present in blood or marrow at baseline. Immunophenotyping must be performed to determine lineage (B-cell, T-cell, or mixed B/T-cell).

Extramedullary Disease in ALL:

- 1 Measurable Extramedullary Disease: Lesions that can be accurately measured in 2 dimensions by CT or MRI.
- 2 Non-measurable Extramedullary Disease: All other lesions including unidimensional lesions, lesions too small to be considered measurable, pleural or pericardial effusion, ascites, bone disease, leptomeningeal disease, lymphangitis, pulmonitis, abdominal masses not confirmed or followed by imaging techniques or disease documented by indirect evidence only (eg, lab values).

For patients with extramedullary disease, baseline disease assessments will be performed using radiologic imaging by CT with contrast covering neck, chest, abdomen, and pelvis within 30 days before the first dose of study treatment. Radiologic scans (ie, contrast CT) will be repeated approximately every 12 weeks \pm 7 days. Up to 6 measurable extramedullary disease lesions (only target lesions >1.0 cm in the longest diameter may be assessed), clearly measurable in 2 perpendicular dimensions, will be followed as target lesions for each patient. Measurable sites of disease should be chosen such that they are representative of the patient's disease. In addition, selection of target lesions should be from as disparate regions of the body as possible when these areas are significantly involved. If additional non-measurable extramedullary disease lesions are present, they can be added as non-target lesions and followed throughout the study. For patients with baseline hepatosplenomegaly, the cranial-caudal measurement of the spleen and longest diameter of the liver will be assessed at screening and all subsequent response evaluations. MRI may be used for imaging assessments if a contrast CT scan is contraindicated or unobtainable. In cases where MRI is desirable, the MRI must be obtained at baseline and at all subsequent response evaluations.

Patients without extramedullary disease will be assessed for response every 4 weeks (\pm 7 days)

Response Assessment (Advani et al 2022)


SWOG 2020; Advani et al 2022):

C1 extramedullary disease status: Complete disappearance of all measurable and non-

measurable extramedullary disease with the exception of lesions for which the following must be true: for patients with ≥ 1 measurable lesion, all nodal masses > 1.5 cm in greatest transverse diameter (GTD) at baseline must have regressed to ≤ 1.5 cm in GTD and all nodal masses ≥ 1 cm and ≤ 1.5 cm in GTD at baseline must have regressed to < 1 cm GTD or they must have reduced by 75% in sum of products of greatest diameters (SPD). No new lesions. Spleen and other previously enlarged organs must have regressed in size and must not be palpable. All disease must be assessed using the same technique as at baseline.

C2 extramedullary disease status: Patient does not qualify for C1 status.

Complete Remission (CR)

- 1 $< 5\%$ marrow aspirate blasts. Blasts can be $\geq 5\%$ if the blasts are found to be myeloid and there is no evidence of lymphoblasts by flow cytometry or immunostaining.
- 2 ANC $\geq 1,000$ cells/mm 3 ; platelets $> 100,000$ cells/mm 3 ; and no blasts in the peripheral blood.
- 3 C1 extramedullary disease status as described above.

Complete Remission with Incomplete Recovery (CR_i)

Same as CR but platelet count may be $\leq 100,000$ cells/mm 3 and/or ANC $\leq 1,000$ cells/mm 3

Partial Remission (PR)

Improvement or no worsening of ALL, as indicated by all of the following:

- 1 No blasts in the peripheral blood
- 2 ANC $\geq 1,000$ cells/mm 3 ; platelets $> 100,000$ cells/mm 3
- 3 Either or both of the following:
 - At least a 50% decrease in the marrow blast percentage, compared to the pretreatment value, and marrow blast percentage $\geq 5\%$ and $\leq 25\%$.
 - C2 extramedullary disease status as described above.

FAILURE - Resistant Disease (RD)

Resistant Disease: Patient survives ≥ 7 days following completion of initial treatment course with persistent leukaemia in the last peripheral blood smear or bone marrow, or with persistent extramedullary disease.

FAILURE - Aplasia

Aplasia: Patient survives ≥ 7 days following completion of initial treatment course then dies while cytopenic, with the last post induction bone marrow aplastic or hypoplastic (ie, $< 20\%$ cellularity) and without leukaemia blasts.

FAILURE - Indeterminate

Indeterminate:

- (a) Patient survives < 7 days after completion of initial treatment course; or
- (b) patient survives \geq 7 days following completion of initial treatment course then dies with no persistent leukaemia in the peripheral smear but no post-induction bone marrow examination.

RELAPSE FROM CR or CRi

Relapse: Reappearance of leukaemia blasts in the peripheral blood; or > 5% blasts in the bone marrow not attributable to another cause (eg, recovery of normal cells following chemotherapy-induced aplasia); or appearance or reappearance of extramedullary disease.

K 1 References

Advani et al 2022

SWOG 2020

SWOG Data Operations Center. Oncology Research Professional (ORP) Manual. Version 6.0 October 2020.

https://crawb.crab.org/txwb/CRA_MANUAL/Vol1/chapter%2011a_Response%20Assessment-Leukemia.pdf (Accessed 8 Dec 2020).

